10.2 Concurrent Therapies

The use of any concurrent medication, prescription or over-the-counter, is to be recorded on the subject's source document and corresponding case report form (CRF) along with the reason the medication was taken.

Concurrent enrollment in another investigational drug or medical device study is not permitted.

10.2.1 Prohibited Medications/Treatments

Prohibited medications, treatments, and activities are outlined in the Exclusion Criteria ([Section 7.4](#)).

10.2.2 Rescue Medications

In the event that rescue medication is required for worsening signs or symptoms of dry eye disease during the course of the study, patients will be provided an appropriate rescue regimen by the investigator/treating clinician, and will be exited from the study.

10.2.3 Special Diet or Activities

No special diets or activities are required for this study.

10.3 Examination Procedures

10.3.1 Procedures to be Performed at Each Study Visit with Regard to Study Objective(s)

10.3.1.1 Visit 1: Screening (Day -14 ± 2)

Pre-CAE®

- Written informed consent form
- Demographic information
- Medical, ophthalmic, and dry eye disease history
- Concomitant medications and procedures
- Inclusion and exclusion criteria
- Urine pregnancy test (for females of childbearing potential)
- Patient symptoms using the Visual Analog Scale
- Ocular Discomfort Score
- OSDI®

- SANDE
- Best-corrected visual acuity
- Vital signs
- Bulbar conjunctival hyperemia scores (Ora Calibra® Conjunctival Redness for Dry Eye Scale)
- Slit-lamp biomicroscopy
- Oculus Keratograph 5® procedures: TBUT and tear meniscus height (selected sites)
- TFBUT
- Sodium fluorescein corneal staining, using the Oxford scale and Ora Calibra® scales
- Lissamine green conjunctival staining, using the Oxford scale
- 15+ minute wait from end of Lissamine staining to start of Schirmer's Test
- Schirmer's without anesthesia
- 90-minute CAE® exposure;
 - Ora Calibra® Ocular Discomfort Scale upon entering the CAE® and every 5 minutes thereafter;

Post-CAE®

- Inclusion and exclusion criteria
- Patient symptoms using the Visual Analog Scale
- Ocular Discomfort Score
- Bulbar conjunctival hyperemia scores (Ora Calibra® Conjunctival Redness for Dry Eye Scale)
- Slit-lamp biomicroscopy
- TFBUT
- Sodium fluorescein corneal staining, using the Oxford scale and Ora Calibra® scales

- Lissamine green conjunctival staining, using the Oxford scale
- Intraocular pressure (IOP)
- Ophthalmoscopy (the dilating drug should not be given until the time of ophthalmoscopy)
- Blood sample collection for Hematology and Chemistry
- Urine sample collection for Urinalysis
- Dispense AXR-159 Ophthalmic Solution Vehicle
- Adverse event query

10.3.1.2 Visit 2: Baseline & Randomization (Day 1)

- Study drug collection
- Medical/medication history update
- Inclusion and exclusion criteria
- Patient symptoms using the Visual Analog Scale
- Ocular Discomfort Score
- OSDI
- SANDE
- BCVA with manifest refraction
- Vital signs
- Bulbar conjunctival hyperemia scores (Ora Calibra® Conjunctival Redness for Dry Eye Scale)
- Slit-lamp biomicroscopy
- Tear Collection (selected sites)

- Oculus Keratograph 5® procedures: TBUT and tear meniscus height (selected sites)
- TFBUT
- Sodium fluorescein corneal staining, using the Oxford scale and Ora Calibra® scales
- Lissamine green conjunctival staining, using the Oxford scale
- 15+ minute wait from end of Lissamine staining to start of Schirmer's Test
- Schirmer without anesthesia
- Intraocular pressure (IOP)
- Randomization
- Blood sample collection for systemic pharmacokinetics (in selected Stage 1 patients)
- Administer AXR-159 Ophthalmic Solution or vehicle in both eyes (must NOT be done before blood and tear sample collection)
- Ora Calibra® Drop Comfort Assessment
- Collect and dispense study drug
- Adverse event query

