15. Diagnosis of hepatitis C infection, human immunodeficiency virus (HIV) infection, sarcoidosis, amyloidosis, active tuberculosis, or graft versus host disease
16. History of anterior segment surgery or trauma that could affect corneal sensitivity (e.g., cataract surgery, refractive surgery or any surgery involving a limbal or corneal incision) in either eye within the 12 months prior to Visit 1
17. Planned anterior segment surgery (e.g., cataract surgery or any surgery involving a limbal or corneal incision) in either eye during the study

18. Known allergy or sensitivity to fluorescein, lissamine green, or the study medication or its components
19. Patient is unlikely to follow study instructions or to complete all required study visits or has a condition or situation that in the investigator's opinion, may put the patient at significant risk, may confound the study results, or may interfere significantly with the patient's participation in the study
20. Patient is an employee at the investigational site or is related to any member of the study staff
21. Patient cannot tolerate multiple blood draws
22. Pregnant, nursing, or females of childbearing potential and not utilizing adequate birth control measures
23. Participation in another ophthalmic clinical trial involving a therapeutic drug or device within the past 30 days
24. Previous exposure to AXR-159 Ophthalmic Solution or Ophthalmic Solution Vehicle.

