7.5 Withdrawal Criteria (if applicable)

Patients can voluntarily withdraw from the study at any time. The investigator and AxeroVision Inc. can withdraw a patient from the study at any time for any reason. Additionally, patients can be discontinued from the study by an investigator if any of the following criteria are met:

- Patient develops (or had an exacerbation of) any medical condition that, in the opinion of the investigator, would put the patient at an unacceptable medical risk or compromised the patient's ability to participate in the study
- Patient is unwilling or unable to continue to comply with study procedures
- Patient becomes pregnant

The study can be stopped at the study site(s) at any time by the site investigator(s). AxeroVision Inc. can stop the study (and/or the study site[s]) with appropriate notification.

If a patient discontinued participation in the study early, every attempt will be made to complete the exit procedures. Notification of early patient discontinuation from the study and the reason for discontinuation should be made to AxeroVision Inc. and clearly documented on the appropriate eCRF.

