10.1.4 Procedures for Final Study Entry

Subjects must meet all inclusion and none of the exclusion criteria.

10.1.5 Methods for Assignment to Treatment Groups:

Prior to initiation of study run-in (at Visit 1), each subject who qualifies for entry will be assigned a screening number. All screening numbers will be assigned in strict numerical sequence at a site and no numbers will be skipped or omitted. If all inclusion and exclusion criteria are met at Visits 1 and 2, each qualifying subject will then be assigned a randomization number at the end of Visit 2.

A randomization schedule will be provided to each investigational site. The randomization schedule will use block randomization stratified by site, such that there will be an approximate equal number of subjects assigned to each of the two treatment arms at each site for the Stage 1, Expansion Cohort. For Stage 1, Cohorts 1-3 patients with signs and symptoms of DED will be randomly assigned in a 4:1 ratio to receive either a single concentration of AXR-159 Ophthalmic Solution or AXR-159 Ophthalmic Solution Vehicle. The site staff will dispense to the patient the study kit labelled with the corresponding randomization number. The randomization number will be recorded on the patient's source document and eCRF. New kits will be dispensed at Visits 2, 3, and 4 based on the subject's randomization. The Sponsor, Investigators, and study staff will be masked during the randomization process and throughout the study.

During the run-in period, the patients will all be supplied with AXR-159 Ophthalmic Solution Vehicle. Patients will be informed that they will receive only vehicle during the 2-week run-in period. Following the run-in period the patient, site personnel, the sponsor and patients will be masked to the treatment assignment for the 3 month treatment period. All study medication will be provided in identical unit of dose vials and cartons to maintain masking of the study.

For both Stages 1 and 2, patients with signs and symptoms of DED will be randomly assigned in a 4:1 (Stage 1, Cohorts 1-3) ratio, a 1:1 (Stage 1, Expansion Cohort) ratio, or to a 2:2:2:2:1:1:1 (Stage 2) ratio to receive either a single concentration of AXR-159 Ophthalmic Solution or AXR-159 Ophthalmic Solution Vehicle.

For the expansion cohort in Stage 1 and Stage 2, subjects will be randomized by strata as follows:

- Site
- Baseline eye dryness score ≥ 60 , < 60
- Baseline inferior corneal staining > 1.5 , ≤ 1.5

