15 APPENDICES

APPENDIX 1: SCHEDULE OF VISITS AND MEASUREMENTS

Procedure	Visit 1 Day -14±2		Visit 2 Day 1	Visit 3 Day 15±2	Visit 4 Day 43± 2	Visit 5 Day 85 ± 2	
	Pre CAE®	Post CAE®				Non CAE®	Post CAE®
Informed Consent / HIPAA	X						
Medical / Medication History and Demographics	X						
Medical / Medication Update			X	X	X	X	
Vehicle Run-in Collection			X				
Study Drug Collection			X	X	X	X	
Review of Qualification Criteria	X	X	X				
Adverse Event Query		X	X	X	X	X	X
Pregnancy Test	X ^a					X ^a	
Visual Analog Scale	X	X	X	X	X	X	X
Ora Calibra® Ocular Discomfort Scale	X	X	X	X	X	X	X
SANDE Questionnaire	X		X	X	X	X	
OSDI® Questionnaire	X		X	X	X	X	
Visual Acuity (ETDRS)	X		X	X	X	X	
Vital Signs	X		X			X	
Bulbar Conjunctival Hyperemia	X	X	X	X	X	X	X
Slit-lamp Biomicroscopy	X	X	X	X	X	X	X
Tear Collection (Selected Sites)			X			X	
Oculus Keratograph 5®	X ^b		X ^b	X ^b	X ^b	X ^b	
TFBUT	X	X	X	X	X	X	X
Fluorescein Staining (Ora & Oxford Scales)	X	X	X	X	X	X	X
Lissamine Green Staining (Oxford Scale)	X	X	X	X	X	X	X
15 Minute Wait Period	X		X	X	X	X	
Schirmer's Test	X		X	X	X	X	
CAE® Exposure	X					X	
Discomfort Grading during CAE® Exposure	X					X	
Intraocular Pressure		X	X	X	X		X
Ophthalmoscopy Exam		X ^c					X ^c
CBC and Differential Blood Draw		X					X
Pharmacokinetic Blood Draw			X ^d		X ^d		
Randomization			X				
Vehicle Run-In Dispensation		X					
Vehicle Run-In Instillation		X					
Study Drug Dispensation			X	X	X		
Study Drug Instillation			X	X	X		X

Procedure	Visit 1 Day -14±2		Visit 2 Day 1	Visit 3 Day 15± 2	Visit 4 Day 43± 2	Visit 5 Day 85 ± 2	
	Pre CAE®	Post CAE®	Non CAE®	Non CAE®	Non CAE®	Pre CAE®	Post CAE®
Ora Calibra® Drop Comfort Assessment			X		X		X
Exit Subject from Study							X

^a To women of child-bearing potential, as defined.

^b TFBUT and Tear meniscus height only; only at selected sites

^c Ophthalmoscopy examination will be dilated at randomization and undilated for Visit 5 unless dilation is necessary

^d Blood samples for pharmacokinetic analysis will only be collected for Stage 1, the first 40 patients in the expansion cohort as follows: Visit 2: pre-dose, Visit 4: pre-dose, 15 min, 30 min, 60 min, 90 min, and 3 hr, & 6 hr post dose.

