16.10 Urine Pregnancy Test

A urine pregnancy test will be conducted for females of childbearing potential at Visit 1 (Day -14 ± 2), Visit 5 (Day 85 ± 2), and may be conducted at an Unscheduled Visit. A listing of urine pregnancy test results will be generated.

17. Interim Analyses

An interim analysis will be performed when the last enrolled patient in Stage 1 completes Month 3 of the Expansion Cohort. There is no plan to stop the study for efficacy on the basis of the interim analysis. However, termination in individual dose groups due to safety, tolerability and/or futility may occur. Statistical significance will not be declared at the time of the interim analysis.

Given the exploratory nature of the study no Type I error adjustments will be made for the interim analysis including the Stage 1 data only.

18. Changes from Protocol-Stated Analyses

There are no changes from the protocol-stated analyses.

19. Revision History

The following revisions were made to SAP Version 2.0.

SAP Section	Revision	Rationale
12.1	Revised compliance calculation to use date of completion/discontinuation rather than date of last in-office instillation	Conservative estimation of compliance for discontinued subjects

12.2	Revised exposure calculation to use date of completion/discontinuation rather than date of last in-office instillation	Conservative estimation of exposure for discontinued subjects
13.1.1	Revised specification of random number seeds for MCMC	Consistency with 13.1.2
13.1.3, 13.1.4, 13.1.5	Revised specification of random number seeds for MCMC	Correction of seed specification

20. Tables

Tables that will be included in the topline delivery are shown in boldface font. Tables that will be included in the interim analysis are qualified as “Stage 1”.

Table Number	Title	Population
TABLE 14.1.1.1	SUBJECT DISPOSITION – STAGE 1	ALL RANDOMIZED SUBJECTS
TABLE 14.1.1.2	SUBJECT DISPOSITION – STAGE 2	ALL RANDOMIZED SUBJECTS
TABLE 14.1.1.3	SUBJECT DISPOSITION – COMBINED STAGE 1 AND STAGE 2	ALL RANDOMIZED SUBJECTS
TABLE 14.1.2.1.1	DEMOGRAPHICS – STAGE 1	MITT POPULATION
TABLE 14.1.2.1.2	DEMOGRAPHICS – STAGE 1	MITT2 POPULATION
TABLE 14.1.2.1.3	DEMOGRAPHICS – STAGE 1	SAFETY POPULATION
TABLE 14.1.2.2.1	DEMOGRAPHICS – STAGE 2	MITT POPULATION
TABLE 14.1.2.2.2	DEMOGRAPHICS – STAGE 2	MITT2 POPULATION
TABLE 14.1.2.2.3	DEMOGRAPHICS – STAGE 2	SAFETY POPULATION
TABLE 14.1.2.3.1	DEMOGRAPHICS – COMBINED STAGE 1 AND STAGE 2	MITT POPULATION

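### No pregnancy test is scheduled at Visit 2, so the only scheduled result is about 14 days old when AXR-159 is first given

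*Protocol*

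**What the plan says.** Protocol section 10.3.1.1 (Visit 1) lists "Urine pregnancy test (for females of childbearing potential". The same item returns in section 10.3.1.5 (Visit 5) and is absent from the lists for Visits 2, 3 and 4. The tables in Protocol Appendix 1 and SAP section 3.2 agree: each marks the test only at Visit 1 pre-CAE and Visit 5 pre-CAE, with the footnote "To women of child-bearing potential, as defined". SAP section 16.10 gives the same schedule: "Visit 1 (Day -14 ± 2), Visit 5 (Day 85 ± 2), and may be conducted at an Unscheduled Visit".

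Exclusion 22 (Protocol section 7.4) reads: "Pregnant, nursing, or females of childbearing potential and not utilizing adequate birth control measures". Section 10.1.5 makes entry depend on both visits: "If all inclusion and exclusion criteria are met at Visits 1 and 2, each qualifying subject will then be assigned a randomization number".

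The run-in is on vehicle for everyone (sections 6.1 and 10.1.5). The first randomized dose is given at Visit 2, where section 10.3.1.2 says: "Administer AXR-159 Ophthalmic Solution or vehicle in both eyes (must NOT be done before blood and tear sample collection". Before randomization, that visit list contains a review of the inclusion and exclusion criteria and a "Medical/medication history update".

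**The concern.** Visit 2 is the last point at which a pregnancy can be found before active drug is given. Eligibility has to hold there, yet the only objective evidence on pregnancy comes from before the run-in. A criteria review and a history update can pick up a pregnancy the woman already knows about. They cannot pick up one that was too early to show at Visit 1 and that she has not recognized.

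The stake is patient safety. The protocol's risk summary describes this as the first use of the compound as an eye drop in humans. Section 7.5 lists "Patient becomes pregnant" among the reasons for discontinuation, section 10.3.1.5 requires immediate sponsor notification and follow-up of the outcome, and section 11.2 counts a congenital anomaly as a serious adverse event.

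**Working it through.** The plan gives no figure of its own on this point. The check compares the visit schedules and uses simple day arithmetic.

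**Inputs**

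- Visit 1 on Day -14 ± 2, with a pregnancy test (Protocol 10.3.1.1).
- Visit 2 on Day 1, randomization and first active dose, no pregnancy test (Protocol 10.3.1.2).
- Visit 5 on Day 85 ± 2, next scheduled pregnancy test (Protocol 10.3.1.5).
- Run-in of 14 days on vehicle (Protocol 6.1), which fits day numbering without a Day 0.

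**Step 1. How pregnancy compares with the other criteria at Visit 2.** The entry criteria in section 7.3 that name both visits (visual acuity, corneal staining, redness, eye dryness, OSDI, Schirmer) are measured again at Visit 2. Pregnancy can also be tested objectively but is not. Section 8.2 has the most current specimen results reviewed before randomization; for pregnancy, the only scheduled result by then is from Visit 1.

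**Step 2. Age of the result at first active dose.**

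- Without a Day 0, Day -14 to Day 1 is 14 days. The window gives 14 - 2 = 12 to 14 + 2 = 16 days.
- If a Day 0 were counted, it would be 15 days (13 to 17).
- With a test on Day 1 before dosing, it is 0 days.

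**Step 3. Time from first dose to the next scheduled test.** 85 - 1 = 84 days (82 to 86). A test at Visit 2 does not change this.

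**Step 4. What a Visit 2 test would add.** Let L be the number of days from conception until the urine test turns positive. The documents give no value, so L is an assumption, taken as equal at both visits. The Visit 1 test finds conceptions at least L days before Visit 1. A Visit 2 test finds those at least L days before Visit 2. The newly covered conceptions lie between (Visit 1 - L) and (Visit 2 - L). The length of that span is Visit 2 - Visit 1 = 14 days (12 to 16), whatever L is. L only moves the span in time. The part that falls inside the run-in is max(0, run-in length - L).

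| Assumed L | Newly covered conception dates, relative to Visit 1 (14-day run-in) | Length of span | Of which in the run-in |
|---|---|---|---|
| 10 days | 10 days before to 4 days after | 14 (12–16) | 14 - 10 = 4 (2–6) |
| 14 days | 14 days before to Visit 1 | 14 (12–16) | 0 (0–2) |
| 21 days | 21 to 7 days before | 14 (12–16) | 0 |

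Over this range the pregnancies gained are mainly those conceived before Visit 1. Conceptions in the last L days before Visit 2 stay undetected even with the added test.

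**The case against.** The strongest reply is that the plan contains no error. The schedule is the same in every place it appears, and neither document requires a test at randomization or limits the age of the result. Several safeguards already apply. Exclusion 22 removes women not using adequate birth control, which leaves contraceptive failure and misreporting. Eligibility and history are reviewed again at Visit 2. Exclusion 19 lets the investigator keep out a patient at significant risk, and section 10.4.2 allows a test at an unscheduled visit. A pathway exists for a pregnancy that does occur. The risk summary and section 3 expect little systemic exposure from the drops, and the compound was well tolerated by the inhaled and intranasal routes. The proposed test also leaves the 84 days of treatment before Visit 5 without a scheduled test.

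Most of this stands as a limit on the size of the point. It does not close the gap. Birth control lowers the chance of pregnancy but does not verify its absence, and the protocol itself tests at Visits 1 and 5 despite that requirement. Unscheduled tests are optional and not tied to randomization. Negligible exposure is an expectation for a first-in-human eye drop, and systemic pharmacokinetics are still to be measured in Stage 1 (sections 8.3 and 12.4.12). The pregnancy pathway acts after exposure, whereas a test before dosing can prevent it.

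**Conclusion.** The concern holds. Nothing in either document schedules a pregnancy test between Visit 1 and the first active dose, so the only scheduled result is then 14 days old (12 to 16, assuming no Day 0). A test at Visit 2 would newly cover a 14-day span of conception dates (12 to 16), provided the detection lag is the same at both visits. The number of women of childbearing potential is not given, so no count or rate of missed pregnancies can be stated. It is probably small.

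This is a recommended improvement rather than an essential correction: a low-probability but potentially serious safety matter that can be addressed at little cost. Confidence is high on the schedule. The size of the benefit cannot be determined from the documents.

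**What to change.** Add the existing urine pregnancy test for women of childbearing potential at Visit 2, with the result read before randomization. Four places need the edit: Protocol section 10.3.1.2, Protocol Appendix 1, the schedule in SAP section 3.2, and SAP section 16.10.

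The cost is one test strip per woman of childbearing potential, from supplies already listed in Protocol section 9.2, plus a urine sample. Visit 2 currently has no urine collection, so the sample is an added step, but no new visit or staff is needed. A woman who tests positive would fail entry at Visit 2.

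The change covers only pregnancies that become detectable between Visits 1 and 2. It should not be presented as covering all run-in conceptions or any that occur during treatment.

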10.3.1.3 Visit 3: 2-Week Follow-up (Day 15 ± 2 Days)

- Study drug collection
- Medical/medication history update
- Patient symptoms using the visual analog scale
- Ocular Discomfort Score
- OSDI
- SANDE

- BCVA with manifest refraction
- Bulbar conjunctival hyperemia scores (Ora Calibra® Conjunctival Redness for Dry Eye Scale)
- Slit-lamp biomicroscopy
- Oculus Keratograph 5® procedures: TBUT and tear meniscus height (selected sites)
- TFBUT
- Sodium fluorescein corneal staining, using the Oxford scale and Ora Calibra® scales
- Lissamine green conjunctival staining, using the Oxford scale
- 15+ minute wait from end of Lissamine staining to start of Schirmer's Test
- Schirmer without anesthesia
- Intraocular pressure (IOP)
- Dispense study drug
- Administer AXR-159 Ophthalmic Solution or vehicle in both eyes)
- Adverse event query

10.3.1.4 Visit 4: Month 1.5 Follow-up (Day 43 ± 2 Days)

- Study drug collection
- Medical/medication history update
- Patient symptoms using the visual analog scale
- Ocular Discomfort Score
- OSDI
- SANDE
- BCVA with manifest refraction

- Bulbar conjunctival hyperemia scores (Ora Calibra® Conjunctival Redness for Dry Eye Scale)
- Slit-lamp biomicroscopy
- Oculus Keratograph 5® procedures: TBUT and tear meniscus height (selected sites)
- TFBUT
- Sodium fluorescein corneal staining, using the Oxford scale and Ora Calibra® scales
- Lissamine green conjunctival staining, using the Oxford scale
- 15+ minute wait from end of Lissamine staining to start of Schirmer's Test
- Schirmer without anesthesia
- Intraocular pressure (IOP)
- Dispense study drug
- Blood sample collection for systemic pharmacokinetics (in selected Stage 1 patients)
 - Collected pre-dose, and at 15, 30, 60, 90, 180, 360 minutes post-dose
- Administer AXR-159 Ophthalmic Solution or vehicle in both eyes (must NOT be done before blood and tear sample collection)
- Ora Calibra® Drop Comfort Assessment
- Adverse event query

10.3.1.5 Visit 5: 3 Month Follow-up (Day 85 ± 2 Days)

Pre-CAE®

- Study drug collection
- Medical/medication history update
- Urine pregnancy test (for females of childbearing potential)

- Patient symptoms using the visual analog scale
- Ocular Discomfort Score
- OSDI
- SANDE
- BCVA with manifest refraction
- Vital signs
- Bulbar conjunctival hyperemia scores (Ora Calibra® Conjunctival Redness for Dry Eye Scale)
- Slit-lamp biomicroscopy
- Tear Collection (selected sites)
- Oculus Keratograph 5® procedures: TBUT and tear meniscus height (selected sites)
- TFBUT
- Sodium fluorescein corneal staining, using the Oxford scale and Ora Calibra® scales
- Lissamine green conjunctival staining, using the Oxford scale
- 15+ minute wait from end of Lissamine staining to start of Schirmer's Test
- Schirmer without anesthesia
- 90-minute CAE® exposure;
 - Ora Calibra® Ocular Discomfort Scale upon entering the CAE® and every 5 minutes thereafter;

Post-CAE®

- Patient symptoms using the Visual Analog Scale
- Ocular Discomfort Score

- Bulbar conjunctival hyperemia scores (Ora Calibra® Conjunctival Redness for Dry Eye Scale)
- Slit-lamp biomicroscopy
- TFBUT
- Sodium fluorescein corneal staining, using the Oxford scale and Ora Calibra® scales
- Lissamine green conjunctival staining, using the Oxford scale
- Intraocular pressure (IOP)
- Ophthalmoscopy
- Blood sample collection for Hematology and Chemistry
- Urine sample collection for Urinalysis
- Administer AXR-159 Ophthalmic Solution or vehicle in both eyes (must NOT be done before blood and tear sample collection)
- Ora Calibra® Drop Comfort Assessment
- Adverse event query
- Study Exit

Adverse Events (AEs) (both elicited and observed) will be monitored throughout the study. All AEs (both elicited and observed) will be promptly reviewed by the investigator for accuracy and completeness. All AEs will be documented on the appropriate CRF.

If a female becomes pregnant during the study, the investigator will notify AxeroVision Inc. immediately after the pregnancy is confirmed and the patient will be exited from the study after appropriate safety follow-up. The investigator will (1) notify the patient's physician that the patient was being treated with an investigational drug (AXR-159 Ophthalmic Solution), and (2) follow the progress of the pregnancy. The investigator must document the outcome of the pregnancy and provide a copy of the documentation to AxeroVision Inc.

